5.2.2.1.2. Data Included

All available data from mITT analysis set, after taking into account all the intercurrent events and applying the intercurrent event strategies specified in Section [5.2.2](#), will be included.

5.2.2.1.3. Assumptions

- Missing Data for HBsAg are Missing at Random (MAR)
- The treatment effect is homogeneous across randomization stratification strata

5.2.2.1.4. Missing Data Handling Rule

Participants who withdraw from the study prior to Week 72 will be considered as non-responders.

If a participant remains in the study after experiencing a major protocol deviation (defined for the purpose of efficacy analyses and is an intercurrent event) and has missing Week 72 value, then the imputation to non-response will be applied. If the value for the endpoint at Week 72 is available, then such data will be used to determine their response status.

For the participants still in the study at Week 72 or for participants that have neither discontinued treatment early nor experienced any major protocol violations (defined for the purpose of efficacy analyses and is an intercurrent event), and HBsAg values missing at Week 72, then the primary

method to handle missing data will be the Multiple Imputation (MI) approach ([Ratitch B. et al., 2013](#)) under the assumption of MAR will be applied to a model for continuous HBsAg log values over time.

The MI model will use all available data and be applied to the continuous log-transformed HBsAg values (not the binary endpoint). Of note, also the pre-ICE data for those subjects who experienced an ICE will be included in the MI model; but for these subjects the response status will be applied according to the ICE strategies before running the MI model.

The model will include treatment, the 2 randomization factors (race [Asian versus non-Asian] and type of NA [TDF/TAF versus ETV]) and the available non-missing log-transformed HBsAg (values < LLOQ, TND or TD will be first substituted following rules described in [Table 3](#)) for each scheduled time point (Week) and the following demographic and baseline characteristics ([King G. et al., & Honaker J. et al.](#)): age, gender, and baseline log-transformed value for HBsAg level.

A total of 200 datasets will be generated where both intermittent and monotone missing HBsAg values will be imputed for each subject relying on non-missing data from all other subjects within the same treatment group. Once the 200 completed datasets are generated by filling in the missing data with samples from the imputation model, the primary endpoint response status (binary variable) will be derived using both imputed and observed HBsAg values at Week 72.

The MH test will be performed for each dataset to generate individual estimates of the difference in proportions and the standard error adjusted on stratification factors. Then the results from these multiple imputed datasets are combined (pooled) for obtaining the overall inference and p-value in a way that accounts for the variability between imputations ([Ratitch B. et al., 2013](#)).

Depending on the amount of missing data, the number of imputed datasets to be generated will be increased appropriately from the planned 200 to ensure robustness in the MI results and relative efficiency ([Graham JW. et al., 2007](#)).

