9.4. Statistical Analyses

9.4.1. Efficacy Analyses

The primary efficacy analysis will be performed when all participants have completed Week 72 or discontinued earlier. The final analysis will be performed when all participants have completed the last study visit (Week 96) or discontinued earlier.

To evaluate the efficacy, the primary analysis set will be the Intent-to-treat (ITT) population (defined in Section 9.3).

All efficacy summaries will be presented with descriptive statistics by intervention arm. If the endpoint is continuous, the descriptive statistics will include the number of participants, mean, standard deviation (SD), median, range and interquartile range. If the endpoint is binary or categorical, the frequency distribution with the number and percentage of participants in each category will be calculated. For time-to-event variables, a summary table including number of participants included in the analysis, number of participants censored, 25th and 75th percentiles and median time-to-event will be shown by intervention arm. Graphic displays will also be used to summarize the data. Summaries will also be presented by randomization stratification factors,

screening HBsAg level (<1,000 IU/mL or \geq 1,000 IU/mL), race (Asian versus non-Asian) and type of NA (TDF/TAF versus ETV).

The baseline measurements are defined as the measurements taken closest to but before the first administration of study intervention on Day 1.

9.4.1.1. Primary Efficacy Endpoint (HBsAg Seroclearance 24 Weeks After Completion of All Study Interventions at Week 48)

The proportion of participants who achieved HBsAg seroclearance at Week 72 (24 weeks after completion of 48 weeks of treatment with study interventions) without restarting NA treatment will be compared between intervention arms at a 1-sided 0.05 alpha. The primary endpoint will be compared between intervention arms using the stratum-adjusted Mantel-Haenszel difference in proportions,²⁵ where the stratification factors screening HBsAg level (<1,000 IU/mL or \geq 1,000 IU/mL), race (Asian versus non-Asian) and type of NA (TDF/TAF versus ETV) determine the strata. The associated 90% confidence interval (CI) for the difference in proportions will also be calculated.

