1.4. Sample Size Justification

The total study sample size is 120 participants who will be randomly assigned to one of the two intervention arms in a 2:1 ratio (JNJ-3989+JNJ-6379+NA: placebo+placebo+NA). Statistical

power to test the primary hypothesis was assessed using the Mantel-Haenszel test with a 1-sided Type 1 error rate of 0.05, assuming the observed percentage of participants with HBsAg seroclearance at Week 72 in the placebo+placebo+NA arm to be 5%. The sample size of 80 participants in the investigational arm and 40 participants in the control arm provides >91% statistical power to detect a $\geq 20\%$ difference in the primary endpoint.

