5.1.1. Level of Significance

All statistical hypothesis tests will be based on one-sided alpha level of 0.05, and 90% confidence interval (CI) will be presented, unless otherwise specified.

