5.2.2. Main Estimand for the Primary Endpoint

Study Objective: To evaluate the efficacy of the study intervention 24 weeks off-treatment.

Scientific Question: in HBeAg negative, virologically suppressed adult population with chronic HBV infection, what is the benefit of JNJ-3989 200 mg+JNJ-6379+NA (Arm 1) for 48 weeks in terms of functional cure 24 weeks after stopping all study interventions compared with NA alone (Arm 2)?

A) Study Intervention:

- Arm 1: JNJ-3989 (200 mg) + JNJ-6379 (250 mg qd) + NA
- Arm 2: Placebo + Placebo + NA

B) Study Population: HBeAg-negative chronic HBV-infected patients who are virologically suppressed by being treated with NA.

C) Variable: Response status defined as participants who meet the criteria defining functional cure at Week 72 (responders) as in Section 5.2.1

D) Intercurrent events:

- Treatment discontinuation prior to Week 48: if the participant discontinued treatment prior to Week 48 then s/he will be considered non-responder (composite strategy).
- Major protocol deviations affecting efficacy: [Attachment 1](#) identifies the deviations considered intercurrent event. Participants with such deviations and who have missing data for the endpoint will be considered as non-responders (composite strategy). For all other deviations not considered intercurrent events, the data are used regardless of the occurrence of major protocol deviations (treatment policy strategy).
- Deaths prior to Week 72 are handled in a composite strategy as participants who die prior to Week 72 will be considered as non-responders.
- NA re-treatment between Week 48 and 72: the participant will be counted as non-responder (composite strategy).

E) Population-level summary: Difference in proportion of participants with functional cure status at Week 72 between study intervention arms.**5.2.2.1. Main Estimator****5.2.2.1.1. Analysis Methods**

The main estimator is constructed using a Mantel-Haenszel ([Mantel N., et al. 1959](#)) test controlling for stratification factors, i.e., screening HBsAg level ($<1,000$ IU/mL or $\geq 1,000$ IU/mL), race (Asian versus non-Asian) and type of NA (TDF/TAF versus ETV) for the difference in proportions between the intervention arms (Arm 1 minus Arm 2). A 2 sided 90% CI of the difference in proportions will be provided.

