5.2.2.2.4. Sensitivity Estimator 4 For the Main Estimand (Tipping Point)

For this sensitivity estimator 4, the same statistical model (stratum-adjusted MH test), and data included will be used as for the main estimator (Section 5.2.2.1). The assumption for missing data and the rule to handle missing data have changed.

5.2.2.2.4.1. Assumptions

- Missing Data for HBsAg are Missing Not at Random (MNAR)
- The treatment effect is homogeneous across strata

5.2.2.2.4.2. Missing Data Handling Rule

For sensitivity estimator 4, after taking into account all the intercurrent events and applying the intercurrent event strategies specified in Section 5.2.2, the tipping point approach with the exhaustive scenario's analysis will be applied.

For participants with missing response data at Week 72, responder status will be imputed in an increasing manner by participant count for each treatment group. Specifically, for each participant with missing data at Week 72, a responder/non-responder status will be imputed starting with the scenario where all participants are non-responders up to the scenario where all participants are responders. This would include all possible scenario combinations of responder/non-responder status for all missing data, including scenarios where participants on JNJ-3989+JNJ-6379+NA have worse outcomes than participants on placebo+placebo+NA. Within the exhaustive scenarios list, the 'worst case scenario' will be one of the cases where all participants with missing Week 72 data in the JNJ-3989+JNJ-6379+NA arm will be imputed to 'non-responders' and all participants with missing data at Week 72 in the placebo+placebo+NA arm will be imputed to "responders". For each scenario, the same statistical model (stratum-adjusted MH test), will be used as for the

main estimator of the comparisons vs control (Section 5.2.2.1.1). A graphical display of the p-value significance will summarize the results across all scenarios for the tipping point analysis.

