5.3.2.1. Binary Endpoints

The number and proportion (%) of participants achieving the endpoints defined in Section 5.3.1.1 will be summarized. The associated 90% CI may also be included.

The following binary endpoints will be compared between treatment arms using a 2-sided 90% CI of the difference in proportions between the treatment groups (Arm 1 minus Arm 2) that will be constructed using a Mantel-Haenszel test controlling for stratification factors, i.e., HBsAg level (<1,000 IU/mL or \geq 1,000 IU/mL), race (Asian versus non-Asian) and type of NA (TDF/TAF versus ETV):

- HBsAg seroclearance:
 - at Week 48
 - at Week 96 (ie, 48 weeks after completion of all study interventions at Week 48) without restarting NA treatment,
 - 24 weeks after stopping all study interventions (regardless when intervention was stopped) without restarting NA treatment, and
 - 48 weeks after stopping all study interventions (regardless when intervention was stopped) without restarting NA treatment

Bar charts will be provided for selected endpoints for proportions (%) in each intervention arm.

Cumulative percentage of participants achieving any given decrease from baseline at Week 72 and Week 96 in HBsAg and HBV DNA (Section 5.3.1.1.5) will be presented graphically.

Subsections below describe the additional analyses planned for only those specific other secondary binary endpoints that require further evaluations.

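### The SAP pools the Mantel-Haenszel difference with an unnamed standard error to get the primary p-value; if the usual non-null variance is used, one-sided type I error is about 11-12% at the plan's 5% rate, not 5%

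*SAP*

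**What the plan says.** Protocol 9.4.1.1 says the primary endpoint "will be compared between intervention arms using the stratum-adjusted Mantel-Haenszel difference in proportions", with the three randomization factors forming the strata and a 90% CI alongside. SAP 5.2.2.1.1 calls the main estimator an MH test controlling for the same factors, cites only the 1959 MH paper, and adds: "A 2 sided 90% CI of the difference in proportions will be provided". SAP 5.2.2.1.4 then describes the multiple-imputation step. In each completed dataset the MH test is used to "generate individual estimates of the difference in proportions and the standard error adjusted on stratification factors", and the results are combined "for obtaining the overall inference and p-value in a way that accounts for the variability between imputations".

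SAP 1.4 states that "power to test the primary hypothesis was assessed using the Mantel-Haenszel test with a 1-sided Type 1 error rate of 0.05", assuming 5% seroclearance on control, 80 versus 40 participants and more than 91% power for a 20-point difference. SAP 5.1.1 fixes the level: "All statistical hypothesis tests will be based on one-sided alpha level of 0.05".

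The sensitivity analyses refer back to the same procedure. For the tipping-point analysis, SAP 5.2.2.2.4 reads "For each scenario, the same statistical model (stratum-adjusted MH test), will be used as for the" main estimator. For secondary binary endpoints, SAP 5.3.2.1 describes a CI of the difference "that will be constructed using a Mantel-Haenszel test controlling for stratification factors".

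Nowhere does either text name the variance estimator, a continuity correction or the CI method.

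**The concern.** Two different tests fit this wording. An MH test in the ordinary sense uses the hypergeometric variance computed under the null (the CMH statistic). That statistic does not itself supply a standard error for a risk difference, and a risk difference with its standard error is what the SAP pools. The usual standard errors for an MH risk difference (Sato, Greenland-Robins) are not computed under the null, and dividing by them gives a Wald test. SAP 5.3.2.1 mixes the two ideas again by building a CI of the difference from an MH test.

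With many responders the choice would hardly matter. Here the plan expects 2 of 40 control responders, and Protocol 2.1 cites loss rates of around 2% to 5% in comparable settings. With few or no control responders the estimated variance of the difference is too small, and the Wald test rejects too often. At stake is the level of the trial's single primary test.

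**Working it through.** **Inputs.** From SAP 1.4 and 5.1.1: 80 versus 40, control rate 5%, planned rate 25%, one-sided 0.05, power above 91%. Not given in the documents, so assumed: stratum prevalences, block size and the share of values imputed.

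**Formulas.** With stratum weights w = n1·n0/N, the MH difference is d = Σw(p1 − p0) / Σw.

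- Null SE = √[Σ n1·n0·m(N − m) / (N²(N − 1))] / Σw, where m is the number of responders in the stratum. Then d/SE equals the CMH z.
- Wald SE, one stratum = √[p1(1 − p1)/80 + p0(1 − p0)/40].

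**The plan's own figure.** Enumerating all 81 × 41 outcomes at 25% versus 5% gives power of 91.7% with the null variance (90.2% by a normal-approximation formula) and 94.9% with Wald. A continuity-corrected null test gives 84.9%. The uncorrected null-variance test fits the stated figure best.

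**One outcome by hand: 3/80 versus 0/40.** d = 0.0375.

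- Wald SE = √(0.0375 × 0.9625/80) = 0.0212, z = 1.77, p = 0.039.
- Null: 80 × 40 × 3 × 117 / (120² × 119) = 0.655; √0.655 = 0.810; Σw = 26.67; SE = 0.0304, z = 1.24, p = 0.108.

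**Exact type I error, unstratified, nominal 5%.**

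| Rate in both arms | Wald | Null variance |
|---|---|---|
| 2% | 9.6% | 0.2% |
| 5% | 11.2% | 2.9% |
| 10% | 8.2% | 3.9% |

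At 5%, 9.9 of Wald's 11.2 points come from trials with 0/40 control responders.

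**Eight strata at 5%.** Simulation with three assumed prevalence patterns and blocks of 6, 100,000 runs each: Sato 11.3-11.5%, Greenland-Robins 12.0-12.4%, null variance 3.5%. With control risk unequal across HBsAg strata (assumed 10% in the low-HBsAg strata, 5% on average): 10.9-11.2%, 11.8-12.5% and 3.4-3.6%. A separate set of runs with other patterns and block sizes gave 10.9-12.7% for the non-null variances and 3.4-4.0% for the null variance.

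**Effect of imputation.** With nothing imputed, the pooled SE is the single-dataset SE, so the figures above need no missing-data assumption. In an illustrative unstratified check (200 imputations, simple arm-level draws in place of the SAP's HBsAg model) with an assumed 1%, 2.5% or 5% imputed, type I error was 11.2%, 10.9% and 10.8% with the Wald SE and 2.9%, 2.8% and 2.9% with the null SE. Pooling does not close the gap.

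**Where the tests disagree (unstratified).** 3-5/80 versus 0/40, 8-9 versus 1, 11-12 versus 2, 14-15 versus 3, 17 versus 4 and 20 versus 5, with Wald the more lenient each time. They agree at the planned result: 20/80 versus 2/40 gives p = 0.0004 (Wald) and 0.004 (null).

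**Chance that only Wald declares success.** 8.3% at 5% versus 5%, 14.6% at 15% versus 5%, 8.7% at 20% versus 5%, and 3.2% at the planned 25% versus 5%.

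**The case against.** The best reply is that the plan does name a test. It speaks of an MH test for the power, for the main estimator and for the analysis of each imputed dataset, and it cites only the 1959 paper. The stated power matches the null-variance test. On that reading the primary test is conservative and nothing is inflated. The paper that the SAP cites on combining multiply imputed categorical data, or the Data Presentation Specification mentioned in its amendment history, may also settle the matter; neither is available here.

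Most of this stands. A reader might infer from the figures that the primary test will run at 11-12%. The documents do not support that: they lean towards the null variance, and the inflated rate depends on a programming choice that they neither state nor exclude. The opposite inference, that the intended test is therefore clear, also goes too far. The quantity actually pooled is a risk difference with a standard error, and the ordinary way of doing that gives the Wald test.

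Two further limits are fair. Sensitivity estimators 2 to 4 assign a single status per participant or scenario and apply the MH test directly, so the pooling wording does not affect them; they share only the missing definition of the test. And the two tests agree at the planned result, so the choice matters when responder counts are low or the effect is smaller than planned.

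**Conclusion.** The omission is certain from the SAP and protocol text; its consequence is conditional. If the pooled standard error is a non-null one, one-sided type I error is about 11-12% at the plan's 5% rate, more than twice the stated level. If it is the null-variance one, the error is about 3.5% stratified (2.9% unstratified). The unstratified figures rest only on the plan's own inputs. The stratified ones also rest on assumed stratum prevalences and block size, and were stable over the ranges tried. This should be fixed, because two programmers could both follow the SAP and report different primary conclusions. It is not evidence that the wrong test will be run.

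**What to change.** In SAP 5.2.2.1.1 and 5.2.2.1.4:

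- Define the SE pooled for the primary p-value as the null-variance one: the square root of the summed stratum hypergeometric variances divided by the sum of n1·n0/N, without continuity correction, and with zero weight for strata that contain only one arm. The rest of the pooling step can stay as it is.
- Keep the MH difference as the point estimate and name the variance used for the 90% CI.
- State that the null-variance p-value governs the primary conclusion if the two disagree. They can: at 3/80 versus 0/40 a Wald 90% interval has lower limit 0.0375 − 1.645 × 0.0212 = 0.003, above zero, while the null-variance p is 0.108.
- Say that MH test means this statistic in the sensitivity, supplementary and per-protocol analyses.

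If a non-null variance is intended, the SAP should say so and justify the level it attains.

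The cost is SAP wording and modest programming, with no change to design or data. Exact unstratified power relative to Wald is lower by about 3 points at 25% versus 5% (91.7% against 94.9%), 9 points at 20% versus 5% (75.8% against 84.4%) and 15 points at 15% versus 5% (48.5% against 63.1%); these gaps come with Wald's inflated level. The null-variance test is conservative at very low rates (0.2% at a 2% rate). In the illustrative pooling check its power was 91.4%, 91.2% and 90.3% with 1%, 2.5% and 5% imputed, so it may fall slightly below 91%. Few values should need imputing, because SAP 2.3, 5.2.2 and 5.2.2.1.4 send most missing outcomes to non-response or out of the mITT set.

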5.2.2.2. Sensitivity Estimators of the Main Estimand

Sensitivity analyses will be conducted by constructing four sensitivity estimators for the main estimand as defined in Section [5.2.2](#). One estimator will test the assumption of homogeneous treatment effect across the 3 randomization stratification factors, and the three other ones will use different missing data imputation rules.

5.2.2.2.1. Sensitivity Estimator 1 For the Main Estimand (Homogeneity Assumption)

Homogeneity will be assessed for the comparison vs control arm. For this sensitivity estimator 1, the same included data, missing data assumption (MAR), and missing data handling rule (multiple imputation) will be applied. The assumption for homogeneity of treatment effect across the stratification factors will be tested and, if heterogeneity is found statistically significant, a different statistical model is used to define the sensitivity estimator.

5.2.2.2.1.1. Assumptions

- Missing Data for HBsAg are Missing at Random
- The treatment effect is non-homogeneous across strata

5.2.2.2.1.2. Analysis Methods

Homogeneity of treatment effect for each stratification factor separately will be tested using the weighted least squares chi-squared statistic (Lui K. J. et al., 2000) for one-way homogeneity. Tests of homogeneity will be assessed at the one-sided 10% level of significance.

Any heterogeneity found to be statistically significant will be explored using the following statistical model for the sensitivity estimator 1.

Statistical model: A logistic regression model on the primary efficacy endpoint using the 3 randomization stratification factors and interaction terms. The model will include intervention arm, screening HBsAg level (<1,000 IU/mL or \geq 1,000 IU/mL), race (Asian versus non-Asian) and type of NA (TDF/TAF versus ETV) as factors, and the intervention arm-by-factor interaction terms.

5.2.2.2.2. Sensitivity Estimator 2 For the Main Estimand (LOCF)

For this sensitivity estimator 2, the same statistical model (stratum-adjusted MH test), and data included will be used as for the main estimator (Section 5.2.2.1). The assumption for missing data and the rule to handle missing data have changed.

5.2.2.2.2.1. Assumptions

- Missing Data for HBsAg are Missing Completely at Random (Barnes A. et al., 2008)
- The treatment effect is homogeneous across strata

5.2.2.2.2.2. Missing Data Handling Rule

For sensitivity estimator 2, participants who withdraw from the study prior to Week 72 will be considered as non-responders. After taking into account all the intercurrent events and applying the intercurrent event strategies specified in Section 5.2.2, if a subject who did not experience any ICEs has missing response status for the primary endpoint then the LOCF approach will be used as follows.

If the HBsAg value is missing at Week 72, the Last Observation Carried Forward (LOCF) in conjunction with the next available observation imputation approach will be used. The non-missing value closest to Week 72 will be selected among the non-missing values which are no earlier than 12 weeks prior to Week 72 or no later than 12 weeks after Week 72. If 2 non-missing laboratory values are equidistant, the later observation will be preferred. If a subject who did not experience any ICE and does not have HBsAg data within \pm 12 weeks of Week 72, then the subject will be considered as a non-responder.

